5. ANALYSIS POPULATIONS

The analysis of efficacy will be performed in the full analysis set (FAS). The principal analysis set for efficacy will be the modified FAS (mFAS). The analysis of safety will be performed in the safety analysis set (SAF). The analysis of pharmacokinetics will be performed in the pharmacokinetic analysis set.

The analysis sets are defined below. For the contents of the data review meeting, refer to a separate materials.

(1) Efficacy analysis sets

1) Randomized subjects (RAND)

2) FAS

The FAS will consist of all randomized subjects except for the following subjects.

- Subjects who have not received study drug even once
- Subjects with no WOMAC pain subscale score (the primary endpoint) at baseline
- Subjects with no WOMAC pain subscale score (the primary endpoint) at any time point after randomization

3) Modified FAS (mFAS)

The mFAS will consist of the FAS, except for the following subjects.

- Subjects who are randomized to 3 mg q4w group
- Subjects who are randomized to 6 mg q8w group

(2) SAF

The SAF will consist of all randomized subjects except for the following subjects

- Subjects who did not receive study drug even once
- Subjects for whom absolutely no post-randomization safety data are available

(3) Self-injection analysis set(SIAS)

The self-injection analysis set will consist of the mFAS, except for the following subjects.

- Subjects who never performed self-injection

(4) Pharmacokinetic analysis set (PK)

The pharmacokinetic analysis set will consist of subjects who have received investigational drug at least once and who had at least one non-missing post-dose serum drug concentration data.

(5) Anti-drug antibody (ADA) analysis set (ADA)

The ADA analysis set will consist of all treated subjects who received investigational drug or comparative drug at least once and who had at least one non-missing post-dose ADA result.

(6) Neutralizing anti-drug antibody (NAb) analysis set (NAb)

The NAb population includes all treated patients who received any amount of study treatment (drug or placebo; Safety Analysis Set), and either tested negative for ADA or tested positive for ADA with at least one non-missing NAb result (either "NAb negative" or "NAb positive") following the first dose of study drug or placebo.

(7) Concentration-Response analysis set (CR)

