8.2.1. Other Efficacy Endpoints

WOMAC pain subscale score, WOMAC physical function subscale score, WOMAC

stiffness subscale score, WOMAC total score , WOMAC individual score and PGA

For the changes from baseline at each assessment time point in the WOMAC pain subscale score, the WOMAC physical function subscale score, the WOMAC stiffness subscale score, the WOMAC total score, WOMAC individual score and PGA, the analysis will be tested using the estimator of mixed effect model for repeated measurement (MMRM) approach. The model will include the treatment group, measurement time point, treatment group and measurement time point interaction, stratification factor K-L grade (2-3 or 4), and stratification factor evaluated joint (knee or hip) as factors, and the corresponding baseline and baseline and measurement time point interaction as covariates. The within-subject correlation structure will be unstructured, and the denominator degrees of freedom for the test statistics of estimated parameters will be approximated using the Kenward-Roger method. In case the model will not converge with the unstructured covariance structure, Heterogeneous Autoregressive (1) (ARH[1]), Heterogeneous Compound Symmetry (CSH), Autoregressive (1) (AR[1]) or Compound Symmetry(CS) covariance structure will be used instead in this order. MMRM that assumes that the missing mechanism is missing at random (MAR) is an analysis method in which missing values are not replaced. This model will be used to estimate the treatment effect in the mFAS when subjects continue receiving treatment through Week 68.

The sample SAS code planned for the analysis is outlined below.

WOMAC score and PGA will be listed. In addition, change from baseline to week 68 in WOMAC pain subscale score, WOMAC physical function subscale score and PGA will be graphed by visit.

SF-36 / EQ-5D-5L

For the changes from baseline at each assessment time point in SF-36 eight subscale summary scores and three component summary scores / EQ-5D-5L visual analogue scale(VAS) and utility index scores, the same analysis method (MMRM) as above will be analyzed. SF-36 / EQ-5D-5L will be listed.

Proportions of subjects with improvement of 30%, 50%, 70% and 90% at each assessment time point compared to baseline in WOMAC pain subscale score, WOMAC physical function subscale score and improvement of 30%, 50% and 70% at each assessment time point compared to baseline in PGA

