8.3. Safety Assessments

Safety assessments will be made on the SAF population.

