8.3.1. Adverse Events

Overall summary of TEAEs / Post-treatment AEs for the following will be conducted.

- Subjects with at least one AE
- Subjects with at least one adverse drug reaction
- Subjects with at least one SAE
- Subjects with at least one serious adverse drug reaction
- Subjects with at least one AESI
- Subjects with at least one severe AE
- Subjects with at least one AE leading to discontinuation of study drug
- Subjects with AE leading to death

The following summaries also will be conducted.

- TEAEs / Post-treatment AEs by SOC and PT
- TEAEs / Post-treatment AEs related to drug reactions by SOC and PT
- TEAESI / Post-treatment AESI by SOC and PT
- TESAEs / Post-treatment SAEs by SOC and PT
- TESAEs related to drug reactions by SOC and PT
- TEAEs leading to discontinuation of study drug by SOC and PT

- TEAEs / Post-treatment AEs by SOC, PT and severity
- TEAEs related to drug reactions by SOC, PT and severity
- TEAEs by SOC, PT and relationship to study drug
- TESAEs by SOC, PT and relationship to study drug
- Identified TEAEs / Post-Treatment AEs by SMQ, HLGT, HLT and PT

Each of the summaries will be done by treatment group and combined MT-5547 at the subject level - multiple occurrences of the same event within a subject will be counted once in the summaries by SOC and PT; multiple occurrences of the same event within a subject will be counted once in the maximum severity category (severe > moderate > mild) and/or maximum drug relationship category (reasonable possibility/no reasonable possibility) and/or the earliest duration.

The following will be listed.

- AE
- AESI
- AE leading to discontinuation of study drug
- SAE
- Death
- Joint replacements

adjudicated arthropathy

The number and percentage of patients with images requiring adjudicated arthropathy as well as the number and percentage of those patients with confirmed adjudicated arthropathy including all available follow-up data after baseline will be summarized by treatment group and combined MT-5547. Subtypes of AAs and outcomes of AAs will also be summarized. Time to event with AA will be analyzed using Kaplan-Meir approach and will be plotted by treatment group. Cox regression model will be used for descriptively comparing each treatment group to placebo by obtaining hazard ratio estimates along with 95% confidence intervals.

Incidence of AA will be summarized by treatment group and combined MT-5547.

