Incidence rate ratio estimates and 2-sided 95% confidence interval will be computed using Generalized Estimating Equations with a log-linked Poisson model via the PROC GENMOD procedure if there are events in the placebo group. The model will specify the use of a Poisson probability distribution with an offset= log (patient-observation period days) and model terms for treatment-as-received and each randomization strata. If there is no event in the placebo group, incidence rate ratio will not be calculated and confidence intervals for the incidence rate difference will be computed using Wald method.

The incidence rate estimates for each arm, the estimates of the incidence rate ratio and incidence rate difference between MT-5547 and placebo will be summarized.

The SAS code planned for the analysis is outlined below.

[REDACTED]

Assessment of self-injection

— Analysis with respect to a comparison of the doses administered by the principal investigator or sub-investigator after treatment week 24 and the self-injections performed after treatment week 24

This analysis will be summarized using the data after treatment week 24 by the principal investigator or sub-investigator and the self-injections and by MT-5547 treatment group excluding MT-5547 3mg q4w and MT-5547 6mg q8w on SAF population.

Overall summary for the following will be conducted.

- Subjects with at least one TEAE
- Subjects with at least one adverse drug reaction
- Subjects with at least one TESAE
- Subjects with at least one serious adverse drug reaction
- Subjects with at least one AESI
- Subjects with at least one severe TEAE
- Subjects with at least one TEAE leading to discontinuation of study drug
- Subjects with TEAE leading to death
- Subjects with at least one abnormal NCS or CS for injection site assessment

The following summaries also will be conducted.

- TEAEs by SOC and PT

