8.3.8. Radiograph

Adjudicated Arthropathy

Overall summary for adjudicated arthropathy will be conducted.

The following summaries for adjudicated arthropathy also will be conducted.

- Subtype of adjudicated arthropathy
- Subtype of adjudicated arthropathy meeting destructive arthropathy

- Incidence rate of adjudicated arthropathy
- Time to first event of adjudicated arthropathy

As regards time to first event adjudicated arthropathy, cox regression model will be used for descriptively comparing each treatment group to placebo by obtaining hazard ratio estimates along with 95% confidence intervals.

Each of the summaries will be done by treatment group and combined MT-5547.

All data will be listed.

Joint Space Width

The following summaries for joint space width will be conducted.

- Non arthropathy adjudication joint with adjudicated arthropathy
- All joint with non adjudicated arthropathy subjects

Joint space width for AA will be summarized by treatment group and combined MT-5547. All data will be listed. Each of the summaries will be done by treatment group and combined MT-5547.

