8.3.13. Joint Replacement

Number and percentage of patients with joint replacement including all available follow-up data after baseline will be summarized by treatment group and combined MT-5547. Time to event with joint replacement including all available follow-up data after baseline will be analyzed using Kaplan-Meir approach and will be plotted by treatment group.

All data will be listed.

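### The Week 68 Cox model for adjudicated arthropathy names no randomisation strata, although the Poisson model for the same events does; a minor gap that bears mainly on 3 mg q4w and 6 mg q8w against pooled placebo

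*SAP*

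**What the plan says.** The Week 68 SAP describes the Cox analysis of adjudicated arthropathy in two places. Section 8.3.1 says a "Cox regression model will be used for descriptively comparing each treatment group to placebo by obtaining hazard ratio estimates", with 95% confidence intervals. Section 8.3.8 repeats it for time to first event: "cox regression model will be used for descriptively comparing each treatment group to placebo by obtaining hazard ratio estimates along with 95% confidence intervals". Neither names a covariate, a stratum or a definition of treatment.

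Later in 8.3.1, the Poisson model for the incidence rate ratio of the same events has "model terms for treatment-as-received and each randomization strata". The strata can be read from the efficacy model in 8.2.1 of the same SAP: "stratification factor K-L grade (2-3 or 4), and stratification factor evaluated joint (knee or hip) as factors".

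On population, section 8.3 states "Safety assessments will be made on the SAF population", and section 5 defines that set broadly: "The SAF will consist of all randomized subjects except for the following subjects" (those never dosed, or with no safety data after randomisation). All five arms and both periods are therefore included. The reporting table in 9.2 lists 3 mg q4w and 6 mg q8w.

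**The concern.** Two models of one safety contrast are specified differently, and no reason is given. Stratified randomisation balances K-L grade and joint only among arms randomised at the same time. Section 3.3 shows that this is not the case for every comparison with placebo: 3 mg q4w and 6 mg q8w were enrolled before the amendment only, 1 mg q8w after it only, and placebo in both periods. Neither Cox passage restricts placebo to concurrent subjects.

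If K-L grade or joint predicts arthropathy and the mix changed between periods, the unadjusted hazard ratio carries part of that difference. A reader who saw it disagree with the adjusted rate ratio could not tell whether drug or case mix was responsible. Adjudicated arthropathy is an adverse event of special interest, so these estimates will be read closely.

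**Working it through.** The documents give no arthropathy rate, event count or hazard ratio, so there is no planned figure to reproduce. The check asks how far the missing strata could move each hazard ratio.

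**Inputs from Week 68 SAP 3.3.** Placebo 182, of whom about 40 pre-amendment and 142 post-amendment; 1 mg q4w the same; 1 mg q8w 142, all post-amendment; 3 mg q4w and 6 mg q8w 57 each, all pre-amendment. Pre-amendment total 40 + 40 + 57 + 57 = 194; post-amendment total 3 × 142 = 426.

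**Assumptions, not in the documents.** 30% of subjects are K-L 4; the arthropathy hazard in K-L 4 is 3 times that in K-L 2–3; arms are well balanced within each stage.

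**1. How a period difference reaches each comparison.** Let D be the K-L 4 share before minus after the amendment. Pooled placebo is a 40:142 mixture, so:
- 3 or 6 mg minus placebo = (142/182) × D = 0.780 D
- 1 mg q8w minus placebo = −(40/182) × D = −0.220 D
- 1 mg q4w minus placebo = about 0, since it has the same mixture and was randomised alongside placebo
- 1 mg q8w minus post-amendment placebo only = about 0

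**2. Chance size of D.** SD(D) = √[0.3 × 0.7 × (1/194 + 1/426)] = 0.0397. The SD of the share difference is then 0.780 × 0.0397 = 0.031 (about 3 points) for 3 or 6 mg, and 0.220 × 0.0397 = 0.009 (about 1 point) for 1 mg q8w.

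**3. Effect on the hazard ratio.** For rare events and no drug effect, the unadjusted hazard ratio is [1 + (h − 1)p_A] / [1 + (h − 1)p_P]. With h = 3 and p = 0.30, the slope on the log scale is 2/1.6 = 1.25 per unit of share difference. The 95% chance ranges are:
- 3 or 6 mg: exp(±1.96 × 1.25 × 0.031) = 0.93 to 1.08
- 1 mg q8w: exp(±1.96 × 1.25 × 0.0087) = 0.98 to 1.02

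**4. A real change of case mix.** Take h from 1.5 to 4, a post-amendment high-risk share of 10–40%, and D from −10 to +20 points. The unadjusted hazard ratio is multiplied by 0.81–1.33 for 3 or 6 mg against all placebo and by 0.91–1.05 for 1 mg q8w against all placebo. Worked case: h = 4, share 20% after and 40% before. The placebo share is 0.20 + 0.220 × 0.20 = 0.244. The factor is 2.2/1.732 = 1.27 for 3 or 6 mg and 1.6/1.732 = 0.92 for 1 mg q8w.

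**5. Does stratifying remove it?** A simulation of that case, with arms scaled up 60 times and a true within-stratum hazard ratio of 3, gave 3.78 unadjusted and 3.06 stratified for 57 against 182 subjects, and 2.65 and 2.95 for 1 mg q8w. The stratified estimates return to about 3, within simulation error.

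**6. Scale against sampling error.** With an assumed 4 and 7 events, SE(log HR) = √(1/4 + 1/7) = 0.627. The 95% interval then multiplies and divides the estimate by exp(1.96 × 0.627) = 3.4.

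**The case against.** The strongest reply is that little is at stake. The analysis is expressly descriptive, section 6.2 rules out formal tests, and an interval spanning a factor of 3.4 either way dwarfs a shift of a few per cent. An adjusted estimate is already planned whenever placebo has events. That K-L grade or joint predicts arthropathy is assumed, and the strata describe only the evaluated joint, whereas protocol 11.2.1 monitors arthropathy at any joint. Dosing in the 3 mg and 6 mg arms was cut short, which no stratification repairs. All of this stands and limits the weight of the point. It does not explain why the two models differ.

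For 1 mg q8w, protocol section 13 limits evaluation to post-amendment data without confining the rule to efficacy. Week 68 SAP 3.3 repeats it, and section 10 declares no changes from the protocol. Against that, the safety section does not restate the rule, and section 1 says the SAP's own details take precedence. Either reading is tenable, which is why the comparator should be stated.

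The redacted SAS code in 8.3.1 might contain strata, but it follows the Poisson text, and the readable Cox text names none.

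A reader might infer much larger imbalances by treating the arms as independent samples: √[0.21 × (1/57 + 1/182)] = 7 points, and √[0.21 × (1/142 + 1/182)] = 5 points. The documents do not support this, because about 40 and 142 of the 182 placebo subjects respectively were randomised alongside those arms. A 10-point imbalance for 1 mg q8w would need a change of about 0.10/0.22 = 45 points between periods.

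**Conclusion.** The inconsistency is real: as written, the Cox hazard ratio is unadjusted and the Poisson rate ratio for the same events is adjusted. The consequence is minor and concentrated in 3 mg q4w and 6 mg q8w against placebo pooled over both periods. There, chance alone gives up to about 7–8% at the 95% range, and a real case-mix change could give more. For 1 mg q8w the chance figure is about 2%, or about nil if the comparison is with post-amendment placebo. For 1 mg q4w it is about nil. These sizes rest on the assumed 30% K-L 4 share, threefold hazard and good balance within each stage. The documents give figures for none of these.

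Two stronger readings are not supported. The hazard ratios for the two continuing doses are not shown to be materially confounded by the strata. Nor is the handling of joint replacement in 8.3.13 an error: "Time to event with joint replacement including all available follow-up data after baseline will be analyzed using Kaplan-Meir approach", and a Cox model there would be an extra analysis, not a correction. This is a cheap, minor improvement.

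**What to change.** In Week 68 SAP 8.3.1 and 8.3.8, specify: Cox model by treatment received, stratified by K-L grade (2-3 or 4) and evaluated joint (knee or hip), as in the Poisson model. In the same place, state for each arm whether it is compared with concurrent placebo or with all placebo subjects, and whether the protocol's post-amendment rule for 1 mg q8w covers safety. If an unadjusted hazard ratio is intended, say so and report the stratified one beside it.

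The data are already collected, so the cost is a sentence or two and one program statement. With few events the stratified interval may be slightly wider. Stratifying removes only K-L and joint mix. Other differences between periods would need concurrent placebo or a period term, which is a further reason to name the comparator.

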For patients with events, number of patient years is calculated up to the date of the first event and for patients without event, it corresponds to the length of the study observation period.

Incidence Rate will be calculated using the formula.

Incidence Rate = the number of patients with event × 100 / sum of observation periods for all patients (days) × 365.25*

* 1 year = 365.25 days

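### The arthropathy rate-ratio rule in the Week 68 SAP guards against an empty placebo arm only; if the active arm has no events, the GEE interval, with its usual empirical standard error, collapses to zero

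*SAP*

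**What the plan says.** Week 68 SAP 8.3.1, under adjudicated arthropathy, sets out two between-group measures.

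- **Rate ratio.** "Incidence rate ratio estimates and 2-sided 95% confidence interval will be computed using Generalized Estimating Equations with a log-linked Poisson model". The condition for fitting it reads "via the PROC GENMOD procedure if there are events in the placebo group". Besides a log observation-days offset, the model has "model terms for treatment-as-received and each randomization strata".
- **Fallback.** "If there is no event in the placebo group, incidence rate ratio will not be calculated"; a Wald interval for the rate difference is given instead.
- **Hazard ratio.** "Cox regression model will be used for descriptively comparing each treatment group to placebo", with 95% limits and no rule for empty arms. Section 8.3.8 repeats this.

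Section 7.1.3.1 counts first events only: "For patients with events, number of patient years is calculated up to the date of the first event". Each patient therefore contributes one record. The outputs are "The incidence rate estimates for each arm, the estimates of the incidence rate ratio and incidence rate difference between MT-5547 and placebo". Section 9.1 prints ratios to three decimals, and section 6.2 says no formal tests of treatment effects will be done. The SAS code for the model is redacted.

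**The concern.** The authors foresaw that a ratio fails when one arm has no events, but they guarded only the denominator. An active arm with no events passes the stated condition as soon as placebo has one, and the model is then fitted to data for which the log ratio has no finite estimate. With one record per patient, there is no within-patient correlation to model, so what GEE adds is the empirical (sandwich) standard error. That standard error does not signal the failure.

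At stake is the stated uncertainty for an adverse event of special interest that has its own analyses in the SAP and is a criterion for discontinuing study drug (Protocol 12.1). A zero-width interval at zero would sit in the table where the data may be compatible with an increased rate.

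**Working it through.** The documents give no arthropathy figure to reproduce, so the check uses the planned arm sizes and an assumed range of event counts and risks.

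**Inputs.** From Week 68 SAP 3.3: placebo 182, 1 mg q4w 182, 1 mg q8w 142, and 57 in each closed arm (3 mg q4w, 6 mg q8w). Assumed: one active arm with no events, 4 events in each other active arm, k = 1, 2, 3 or 5 on placebo, and about 477 days of follow-up with 15% of patients followed for less.

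**Why the interval collapses.** Without strata, the empirical variance of an arm's log rate is Σ(y − μ)² / (Σμ)².

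- Placebo with k events: about k / k² = 1/k.
- Empty arm of n patients with a common fitted mean m: n·m² / (n·m)² = 1/n, however small m becomes.
- Hence SE ≈ sqrt(1/k + 1/n). For q8w and k = 1, sqrt(1 + 1/142) = 1.004.
- The model-based variance for the empty arm is 1/(n·m), which goes to infinity.

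**Refit.** A GEE Poisson model (log link, log-days offset, independence) gave log ratios of about −21 to −22 for an empty q8w arm. For k = 1: exp(−21.1 ± 1.96 × 1.00), that is 1e-10 to 5e-9. Every scenario printed 0.000 (0.000-0.000), with or without two binary strata. Stopping the unstratified fit by hand at 8, 12, 20 or 25 iterations left the empirical SE unchanged (1.004 each time for k = 1), and the upper limit was below 0.01 even at iteration 8. The model-based SE grew from 46 at iteration 8 to over 10^5 at iteration 25.

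**What the data would support.** With 0 active and k placebo events, the exact upper limit for the active share of events is p = 1 − 0.025^(1/k). The ratio limit is p/(1 − p) × placebo time / active time. For k = 1: 0.975/0.025 = 39, and 39 × 182/142 = 50. Exposure is taken as proportional to arm size.

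| Placebo events | GEE empirical SE (q8w) | GEE table entry | Exact upper limit, q8w | Exact upper limit, 57-patient arm |
|---|---|---|---|---|
| 1 | 1.00 | 0.000 (0.000-0.000) | 50 | 125 |
| 2 | 0.71 | 0.000 (0.000-0.000) | 6.8 | 17 |
| 3 | 0.58 | 0.000 (0.000-0.000) | 3.1 | 7.7 |
| 5 | 0.46 | 0.000 (0.000-0.000) | 1.4 | 3.5 |

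**How often this could arise.** The chance that an arm of n is empty at risk r is (1 − r)^n. The relevant event is joint: placebo has at least one event and the active arm has none. At r = 1% in all arms, placebo has an event with probability 0.839, and the empty-arm chances are 0.161 (q4w) and 0.240 (q8w). So 0.839 × [1 − (1 − 0.161)(1 − 0.240)] = 0.30.

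| Placebo has an event, and: | Placebo risk 0.5% | 1% | 2% |
|---|---|---|---|
| at least one 1 mg arm empty, equal risk | 42% | 30% | 8% |
| at least one 1 mg arm empty, active risk doubled | 22% | 7% | 0.4% |
| a given 57-patient arm empty, equal risk | 45% | 47% | 31% |
| combined 1 mg arms (324) empty, equal risk | 12% | 3% | 0.1% |

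**The case against.** **The code is not visible.** The choice of standard error, and any handling of empty arms, may sit in the redacted SAS code. A model-based error would give 0 to effectively infinity, which is uninformative but does not suggest protection. The refit was in Python; PROC GENMOD might stop with a warning. This stands as a limit on certainty about what would be printed. It does not supply the missing rule, because the visible text settles neither outcome.

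**The comparisons are not fixed.** Section 8.3.1 speaks of MT-5547 against placebo and of summaries by treatment group and combined. If only the combined 1 mg group gets a ratio, the problem is rare. The closed-arm figures matter only if those arms get their own ratios, which the text does not clearly promise.

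**The harm is contained.** The analysis is descriptive. Counts, percentages, Kaplan-Meier curves, per-arm rates and the rate difference appear in the same section. A reader might infer that the output as a whole would declare the drug protective beyond doubt. It would not: 0/142 would stand near 1/182. A several-fold increase remains compatible with the q8w data only at 1 to 3 placebo events. By 6 placebo events the exact upper limit is 1.09, and from 7 (0.89) the direction is supported and only the precision is false.

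**Importance and likelihood can be overread.** A reader might call arthropathy the main identified risk. Protocol 11.2 lists it as one of three events of special interest, and 11.2.3 applies the term identified risk to altered peripheral sensation. Nor can one say that empty arms are likely in general: the documents give no rate, and for the two 1 mg arms the chance falls to 8% at 2% risk even with equal risks.

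**Conclusion.** Wrong as written. The condition on the rate ratio looks at one arm when it needs to look at both. Followed literally with the empirical standard error that GEE normally supplies, it yields a zero-width interval at zero in a situation where, for q8w, the exact upper limit ranges from about 50 (one placebo event) to 1.4 (five).

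The conclusion that a rule is missing rests on the text alone. The collapsed interval rests on the empirical standard error. The exact limits rest on exposure proportional to planned arm size, and the probabilities on assumed risks of 0.5% to 2%. The Cox hazard ratio has the same gap in its wording; that model was not refitted, so no figure is attached to it. Because the analysis is descriptive and the rates and differences are shown beside the ratio, this is a minor-to-moderate correction.

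**What to change.** Amend Week 68 SAP 8.3.1 so that the rule depends on both arms of each comparison:

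- **Both arms have events:** GEE Poisson model as planned.
- **Exactly one arm has none:** exact conditional (person-time) rate-ratio limits in place of the GEE interval.
- **Either arm has none:** also report the rate difference, with an exact or score-type interval in place of Wald.
- **Neither arm has events:** report only the rates and that difference. The conditional ratio is undefined here, and the Wald interval would itself be 0 to 0.
- **Cox model with an empty arm:** profile-likelihood or Firth limits, or a statement that the hazard ratio is not estimable.

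The SAP should also name the comparisons that get a ratio.

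The trigger should be zero events, where the failure is shown, and not a small count. A cutoff of fewer than 5 in either arm would be met 95% to 100% of the time for q8w against placebo at equal risks of 0.5% to 2%, and would in practice displace the strata-adjusted model.

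The cost is a few sentences and a few lines of code, wider intervals, and no strata adjustment in the zero-event case.

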6.2. Statistical Tests

All formal statistical tests of treatment effects will not be done. Point estimates will be accompanied with two-sided 95% CIs where applicable.

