7.1.3.1. Adverse Events

Adverse events will be coded according to the MedDRA version 20.1

(1) Treatment Emergent Adverse Events/ Treatment Emergent Serious Adverse Events (TEAEs/TESAEs)

An AE/SAE is classified as treatment emergent if it newly occurred after the first dose of study drug or if a pre-dose event increases in severity following the first dose of study drug during on-treatment period.

(2) Post-Treatment Adverse Events/ Treatment Serious Adverse Events

An AE/SAE is classified as post-treatment if it newly occurred after the on-treatment period or if the event after the on-treatment period increases in severity.

(3) Adverse Drug Reaction

A TEAE is considered “adverse drug reaction” if it has been assessed as having a “reasonable possibility” in relationship to the study drug.

(4) Adverse Event of Special Interest(AESI)

Adjudicated arthropathy(AA), sympathetic nervous system dysfunction, altered peripheral sensation, destructive arthropathy(DA) are defined as adverse events of special interest (AESI) for the sake of investigating the safety profile of MT-5547.

(5) Identified and Potential Adverse Events

Following are defined as identified and potential adverse event for the sake of investigating the safety profile of MT-5547.

- Arthralgia related event
 - (PT) Arthralgia
 - (PT) Osteoarthritis
 - (PT) Arthritis
 - (PT) Joint stiffness
 - (PT) Joint swelling
 - (PT) Joint effusion
 - (PT) Synovitis
- Bone fractures related event
 - Any PT containing “fracture” but excluding Tooth Fracture and Subchondral Insufficiency fracture (that have been identified to be AAs)
- Joint swelling related event
 - (PT) Joint Swelling
 - (PT) Joint Effusion
- Altered peripheral sensation related event
 - (HLGT) Peripheral Neuropathies
 - (HLT) Paraesthesia and dysaesthesia
 - (HLT) Sensory abnormalities NEC
 - (PT) Myalgia
 - (PT) Hyperreflexia
 - (PT) Hyporeflexia
 - (PT) Areflexia

- Sympathetic nervous system dysfunction related event
 - (HLT) Autonomic nervous system disorders
 - (HLT) Cardiac conduction disorders
 - (PT) Syncope
- Hypersensitivity / anaphylaxis related event
 - (SMQ) Angioedema
 - (SMQ) Anaphylactic reaction
 - (SMQ) Hypersensitivity
 - (PT) Erythema
 - (PT) Prurigo
 - (PT) Pruritus
 - (PT) Pruritus Generalised
 - (PT) Rash Papular

(6) Duration of Adverse Events

Duration of Adverse Events (days) = AE stop date – AE start date + 1

(7) Incidence Rate (per 100 patient-years)

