9.2. Treatments to Report

Treatment	For TFLs
MT-5547 1 mg q8w	MT-5547 1 mg q8w
MT-5547 1 mg q4w	MT-5547 1 mg q4w
MT-5547 1 mg q4w and MT-5547 1 mg q8w	MT-5547 Combined
MT-5547 3 mg q4w	MT-5547 3 mg q4w
MT-5547 6 mg q8w	MT-5547 6 mg q8w
Placebo	Placebo
Placebo group and all active dose levels	Total

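### With no placebo arthropathy events, the Week 68 SAP's Wald interval for the rate difference is [0, 0] at 0 vs 0, and its upper limit is too low at 1 to 4 active events

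*SAP*

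**What the plan says.** Section 8.3.1 of the Week 68 SAP compares adjudicated arthropathy between arms in three ways.

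- **Rate ratio.** If placebo has events, it comes from a log-linked Poisson model fitted by generalized estimating equations. If placebo has none, "incidence rate ratio will not be calculated and confidence intervals for the incidence rate difference will be computed using Wald method". The trigger is the placebo count alone, so 0 vs 0 is included.
- **Rate difference.** The "incidence rate difference between MT-5547 and placebo will be summarized".
- **Time to event.** "Cox regression model will be used for descriptively comparing each treatment group to placebo by obtaining hazard ratio estimates along with 95% confidence intervals".

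The section also states: "Incidence of AA will be summarized by treatment group and combined MT-5547". Section 9.2 defines the combined group as "MT-5547 1 mg q4w and MT-5547 1 mg q8w".

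Section 7.1.3.1 counts each patient once: "For patients with events, number of patient years is calculated up to the date of the first event". Section 6.2 says no formal tests will be done and adds: "Point estimates will be accompanied with two-sided 95% CIs where applicable". No exact, score or continuity-corrected interval is named, and there is no separate rule for zero events in both arms. The SAS code for this analysis is redacted.

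**The concern.** Wald is assigned to the one case where it works worst. It estimates the placebo variance by the placebo count, so with no placebo events that arm contributes no uncertainty, however short its follow-up. With no active events either, the whole variance estimate is zero.

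In this case the plan has no fallback. The rate ratio is dropped, and the Cox hazard ratio has no finite estimate when placebo has no events. The Wald interval is therefore the only between-arm interval a reader would get. Adjudicated arthropathy is an adverse event of special interest (SAP 7.1.3.1) and a criterion for stopping study drug (protocol 12.1). For such an event the upper limit matters most, because it shows how much excess risk the data leave open.

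**Working it through.** The plan states no figure for this interval, so there is nothing to reproduce. It also gives no arthropathy rate, so all counts and rates below are assumptions.

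**Inputs.** Planned sizes (SAP 3.3): 182 on 1 mg q4w, 142 on 1 mg q8w, 182 on placebo; combined active 182 + 142 = 324. Follow-up to Week 68, taken as complete unless stated. Person-time in patient-years (PY): 182 × 68/52 = 238; 142 × 68/52 = 186; 324 × 68/52 = 424; 70% of 238 = 167. Two-sided 95%, z = 1.96.

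**1. Algebra.** Wald is d ± 1.96√(x1/T1² + x0/T0²), with d = x1/T1 − x0/T0. At x0 = 0 it becomes (x1 ± 1.96√x1)/T1. At x1 = 0 that is [0, 0] for any T1.

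**2. Upper limit in events.** Multiplied by T1, the limit no longer depends on person-time. Exact limit: χ²(0.975; 2x1 + 2)/2. Mid-P limit: the mean at which P(X < x1) + 0.5·P(X = x1) = 0.025.

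| Active events (placebo 0) | Wald | Mid-P | Exact | Wald/mid-P | Wald/exact |
|---|---|---|---|---|---|
| 1 | 2.96 | 4.93 | 5.57 | 60% | 53% |
| 2 | 4.77 | 6.61 | 7.22 | 72% | 66% |
| 3 | 6.39 | 8.16 | 8.77 | 78% | 73% |
| 4 | 7.92 | 9.65 | 10.24 | 82% | 77% |

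**3. Intervals per 100 PY, 238 PY per arm.** MOVER takes exact limits (l, u) for each arm's rate r: lower d − √((r1 − l1)² + (u0 − r0)²), upper d + √((u1 − r1)² + (r0 − l0)²). The score interval inverts the test with the constrained Poisson estimate.

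| Active vs placebo | Wald | MOVER-exact | Score |
|---|---|---|---|
| 0 vs 0 | [0, 0] | [−1.55, 1.55] | [−1.61, 1.61] |
| 1 vs 0 | [−0.40, 1.24] | [−1.18, 2.34] | [−1.19, 2.38] |
| 3 vs 0 | [−0.17, 2.69] | [−0.58, 3.68] | [−0.35, 3.71] |

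Upper limits at 1 vs 0, Wald against MOVER-exact: q8w (186 PY) 1.59 and 3.00; 70% follow-up (167 PY) 1.78 and 3.34.

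**4. How often the upper limit falls below the true difference.** These are Poisson sums over x1 given no placebo events, with 238 PY per arm and a true placebo rate of 0 unless stated. The nominal value is 0.025.

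| True active rate per 100 PY | From 0 vs 0 | From 1 or more active events |
|---|---|---|
| 0.5 | 0.304 | 0 |
| 1.0 | 0.093 | 0 |
| 1.5 | 0.028 | 0.101 (0 at placebo rate 0.4) |
| 2.0 | 0.009 | 0.041 |
| 3.0 | 0.001 | 0.074 (0.026 at placebo rate 0.4) |

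At rates 0.5 and 1.0 every miss comes from 0 vs 0. A single active event adds misses only when the true difference exceeds 1.24 per 100 PY.

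**5. How often the rule applies.** P(no placebo events) = exp(−rate × 238/100): 0.62 at 0.2 per 100 PY, 0.39 at 0.4, 0.09 at 1.0, 0.01 at 2.0. With placebo rate 0.2 and active rate 0.5, P(0 vs 0) is 0.19 and P(0 placebo and 1 to 4 active) is 0.43; with active rate 1.0 they are 0.06 and 0.51.

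**6. Lower limit (secondary).** It ignores placebo person-time. At equal person-time this does no harm: lower-limit misses are 0.001 to 0.011 at active rates 0.5 to 2.0. If the combined group (424 PY) is compared with placebo (238 PY), misses are 0.002 to 0.020 at placebo rates 0 to 0.2, and 0.027 to 0.064 at 0.4. At 4 vs 0, Wald gives [0.02, 1.87], MOVER-exact [−0.75, 2.42] and score [−0.67, 2.43]. This error overstates harm, so it is separate from the upper-limit problem.

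**The case against.** The strongest reply is that little depends on this interval. The Week 68 analysis is descriptive and no decision rule uses it. Counts, per-arm rates, Kaplan-Meier curves and listings are also reported. With no placebo events, the exact-based upper limit is simply the active arm's own Poisson limit, which a reader could work out from the reported count and person-time. All of this stands and limits the consequence. It does not make the stated interval correct, and no method is named for a per-arm interval.

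The redacted SAS code might handle 0 vs 0 differently. That also stands, so [0, 0] is what the wording gives rather than proven output. But with equal arms a continuity correction of (1/T1 + 1/T0)/2 adds only one event to the upper limit: 1.00, 3.96, 5.77, 7.39 and 8.92 events at 0 to 4 active events, against exact limits of 3.69, 5.57, 7.22, 8.77 and 10.24. The shortfall remains.

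The exact limit is a conservative yardstick, and the miss rates in step 4 are conditional on no placebo events. Against mid-P the shortfall is smaller but still clear. Multiplied by P(no placebo events), the total of 0.049 at active rate 2.0 becomes 0.049 × 0.62 ≈ 0.03 at placebo rate 0.2 and 0.049 × 0.39 ≈ 0.02 at 0.4. If placebo events are common, the rule may never be used.

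The lower-limit point is weak: it needs unequal person-time, a placebo rate near 0.4, and a combined-versus-placebo contrast that the SAP implies rather than spells out. It would not justify a change alone.

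**Conclusion.** The concern holds. As worded, the rule gives [0, 0] at 0 vs 0, and at 1 to 4 active events its upper limit is 53% to 77% of exact (60% to 82% of mid-P). Both results follow from the formula and do not depend on arm size, follow-up or dropout. The limits per 100 PY assume the planned sizes and complete 68-week follow-up unless stated. The miss rates, and the chance that the rule is used at all, rest on assumed arthropathy rates.

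The change should be made, but its reach is narrow: one descriptive safety interval. Efficacy is unaffected, and no fault is claimed in the rule for the case where placebo has events.

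**What to change.** In Week 68 SAP 8.3.1, replace Wald for the case of no placebo events, stating that 0 vs 0 is included, by an interval that does not collapse at zero counts. MOVER with exact Poisson limits per arm and the Miettinen-Nurminen score interval both serve. Their upper limits are nearly the same (2.34 and 2.38 at 1 vs 0; 3.68 and 3.71 at 3 vs 0), and both also lower the combined-group lower limit. Name one in advance. State that the Cox hazard ratio will be reported as not estimable in this case.

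The cost is one sentence and a few lines of code. Intervals become wider and upper limits higher. The exact-based option is conservative, with coverage of about 0.98 to 1.00 in the equal person-time scenarios examined.
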